Study Population:	Subjects with active, moderate to severe Crohn's Disease (CD). The following inclusion criteria apply: • Males and females 18 to 75 years of age. • Signed fully informed consent provided as per this protocol. • Diagnosis of Crohn's Disease confirmed by endoscopy or radiography and/or histology at least 6 months prior to randomization into the study. • CD involving the ileum and/or colon • Moderately to severely active CD (Crohn's Disease Activity Index (CDAI) score of ≥ 220 and ≤450) at baseline. • Current treatment with at least one of the following therapies: • Oral 5-aminosalicylic acid (5-ASA) compounds • Dose must be stable for at least 4 weeks before baseline • Corticosteroid therapy • Dose must be stable for at least 2 weeks before baseline • Azathioprine or 6-mercaptopurine (6-MP) or methotrexate • Dose must be stable for at least 8 weeks before baseline • Infliximab or adalimumab • Dose must be stable for at least 14 weeks before baseline • White blood cell count ≥ 3.5x10° at screening. • Active Crohn's disease, defined by at least one of the following: C-reactive protein > Upper Limit of Normal (ULN) at screening, OR radiographic (MRE or CTE) or endoscopic confirmation of the presence of active CD within 5 weeks of screening visit. • Subject agrees to use the following effective contraceptive methods only • diaphragm, cervical cap, contraceptive sponge or condom with spermicidal foam/gel/cream/suppository • IUD/IUS • progestogen injection (Depo-Provera®) throughout the study and for at least 6 weeks after last study drug administration, unless subject or partner of subject is post-menopausal or otherwise incapable of becoming pregnant by reason of surgery or tubal ligation, or has had a vasectomy. In regions where local regulatory						
	contraceptive requirements differ, the ICF will reflect local policies. The following key exclusion criteria apply: Crohn's disease involvement isolated to the mouth, upper gastrointestinal tract, or anus.						

	History of total colectomy with ileorectal anastomosis or a proctocolectomy.				
	 Presence of active fistulizing Crohn's Disease or healed fistula within 2 m prior to screening. 				
	Subject has postoperative stoma, ostomy, or ileoanal pouch.				
	Subject has short bowel syndrome.				
	Subject is scheduled for surgical bowel resection.				
	 Subject has known symptomatic obstructive strictures or bowel perforation in the 6 months prior to screening. 				

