6. STATISTICAL METHODOLOGY

6.1 Statistical and Analytical Issues

6.1.1 Statistical Methods

Descriptive statistics summary results will be produced and presented for all the data collected on the different assessments that include demographics, baseline characteristics, concomitant medications, efficacy, and safety endpoints. Continuous data summary descriptive statistics will

include the number of observations, means, standard deviations, medians, and ranges. Categorical variables will be summarized with frequencies and percentages.

The primary hypothesis testing will be two-sided statistical significance testing (alpha level = 0.05) comparing active treatment to placebo and mainly dedicated to assessing the primary endpoint and the key secondary endpoints. Point and interval estimates (95% confidence intervals) will be calculated and presented by treatment group for each parameter. Computed p-values will be rounded to four decimal places; p-values less than 0.0001 will be presented as '< 0.0001' and p-values greater than 0.9999 will be presented as '> 0.9999' in the tables.

All statistical analyses will be performed using SAS statistical software (Version 9.3 or an updated latest higher version available at the time of analysis). Adverse events will be coded using the most recent MedDRA version available at the time of analysis and the version used will be footnoted in the respective summary tables. Concomitant medications will be coded using the most recent version of World Health Organization (WHO) Drug dictionary.

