6.5.2 Laboratory Parameters

Laboratory assessments will include:

Biochemistry: total protein, gamma glutamyl transferase (GGT), lactate dehydrogenase (LDH), sodium, potassium, chloride, magnesium, glucose, total bilirubin, AST(SGOT), ALT(SGPT), alkaline phosphatase, amylase, albumin, BUN, calcium, creatinine, uric acid, HCO₃, total cholesterol, creatinine phosphokinase, and inorganic phosphorous.

Hematology: RBC count, hemoglobin, hematocrit, platelet count, WBC count, WBC differential.

Urinalysis: Pregnancy, pH (dipstick), specific gravity (dipstick), glucose (dipstick), protein (dipstick), ketones (dipstick), blood (dipstick), Nitrites, Leucocytes and sediment microscopy if indicated by the dipstick.

Laboratory results will be presented in listings in measured units and summaries in conventional units.

Continuous laboratory values will be summarized descriptively by treatment group over time for each visit and as change from baseline to each visit. Categorical laboratory values will be summarized as the number and percentages of subjects in each category by treatment group over time for visit.

Laboratory parameters will also be summarized in shift tables by treatment, to determine the number and percentage of subjects with measurements classified in a particular category at each post-baseline visit with reference to the same classification at baseline. Biochemistry and hematology parameters (which are continuous in nature) will use the classifications of low, normal, and high relative to normal ranges, whereas appropriate categories will be selected for urinalysis parameters (which are categorical in nature), for example, normal and abnormal.

Subjects missing a value at any time point will be excluded from the summary statistics for that time point. If a subject has more than one value at any time point, then the latest non missing value will be used for summarization. All values will be presented in the data listings.

Listings of all individual laboratory data, indicating any values out of the normal range will be produced. A listing of lab parameter values flagged as abnormal will also be provided.

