Table 14.3.4.2	Biochemistry Laboratory Data – Shift from Baseline: Safety Population
Table 14.3.4.3	Hematology Laboratory Data – Observed and Change from Baseline: Safety Population
Table 14.3.4.4	Hematology Laboratory Data – Shift from Baseline: Safety Population
Table 14.3.4.5	Urinalysis Laboratory Data – Observed and Change from Baseline: Safety Population
Table 14.3.4.6.1	Urinalysis Laboratory Data – Shift from Baseline – Numerical Tests: Safety Population
Table 14.3.4.6.2	Urinalysis Laboratory Data – Shift from Baseline – Categorical Tests: Safety Population
Other Safety Assessments	
Table 14.4.1	Vital Signs – Observed and Change from Baseline to Weeks 26 and 52: Safety Population
Table 14.4.2	Uveitis Assessment at Baseline, Week 26 and Week 52: Safety Population

Listings:

Listing Number	Title
Listing 16.2.1.1	Subject Disposition and End of Participation in the Trial: Intent-to-Treat Population
Listing 16.2.1.2	Inclusion and Exclusion Criteria: Intent-to-Treat Population
Listing 16.2.2.1	Major Protocol Deviations: Intent-to-Treat Population
Listing 16.2.2.2	Analysis Populations: Intent-to-Treat Population
Listing 16.2.3.1	Subjects Excluded from Efficacy Analysis
Listing 16.2.4.1	Demographics and Baseline Disease Characteristics: Intent-to-Treat Population
Listing 16.2.4.2	Crohn's Disease History: Intent-to-Treat Population
Listing 16.2.4.3	Medical History (excluding Crohn's disease): Intent-to-Treat Population
Listing 16.2.4.4	Surgical History of Crohn's disease: Intent-to-Treat Population
Listing 16.2.4.5	Prior anti-TNF Agents Use: Intent-to-Treat Population
Listing 16.2.4.6	Prior Alcohol Consumption and Tobacco Use: Intent-to-Treat Population
Listing 16.2.4.7	Prior and Concomitant Medications Use: Intent-to-Treat Population
Listing 16.2.4.8	Prior and Concomitant Steroids Use: Intent-to-Treat Population
Listing 16.2.4.9	Crohn's Disease Prior and Concomitant Medications: Intent-to-Treat Population
Listing 16.2.4.10	Concomitant Procedures: Intent-to-Treat Population
Listing 16.2.5.1	Drug Exposure and Compliance: Intent-to-Treat Population
Listing 16.2.6.1	Crohn's Disease Activity Index (CDAI) Score: Intent-to-Treat Population
Listing 16.2.6.2	Remission, Response and Steroid Free by Time On study: Intent-to-Treat Population
Listing 16.2.6.3	SF-36 Questionnaire Domain and Component Scores: Intent-to-Treat Population
Listing 16.2.6.4	Inflammatory Bowel Disease Questionnaire (IBDQ) Score: Intent-to-Treat Population

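### No planned laboratory table counts, by arm, subjects with a marked or worst post-baseline abnormality, because biochemistry and hematology shifts are classed only as low, normal or high

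*SAP*

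**What the plan says.** SAP 6.5.2 sets the rule for the shift tables. Subjects are "classified in a particular category at each post-baseline visit with reference to the same classification at baseline", and biochemistry and hematology parameters "will use the classifications of low, normal, and high relative to normal ranges". Urinalysis has its own categories and is not part of this point.

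The table list in SAP 8.1 gives each panel one shift table: Table 14.3.4.2, "Biochemistry Laboratory Data – Shift from Baseline: Safety Population", and Table 14.3.4.4, "Hematology Laboratory Data – Shift from Baseline: Safety Population". The titles name no categories; the three-way classification comes from 6.5.2.

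The other planned laboratory outputs are:
- Tables 14.3.4.1 and 14.3.4.3, in which continuous values are "summarized descriptively by treatment group over time for each visit and as change from baseline to each visit". Under SAP 6.1.1 such summaries "include the number of observations, means, standard deviations, medians, and ranges".
- Listings 16.2.8.1 and 16.2.8.2. Section 6.5.2 states: "Listings of all individual laboratory data, indicating any values out of the normal range will be produced". It also plans a listing of values flagged as abnormal.

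Neither 6.5.2 nor 8.1 mentions a toxicity grade, a multiple of the normal limit, a criterion for a marked abnormality, or a worst post-baseline value.

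**The concern.** The protocol synopsis names changes from baseline in hematology and chemistry as part of the safety outcome, and treatment lasts up to 52 weeks. For such data the useful between-arm question is usually how many subjects in each arm had a marked abnormality at any time, and how many got clearly worse than they were at entry.

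A three-category shift table answers a different question: how many subjects were outside the normal range at a given visit. Two kinds of information drop out. Size is lost, because everything beyond the limit is one category. Worsening from an abnormal start is lost, because the category does not change. If the arms differed in marked abnormalities, no laboratory table would put that difference in front of the reader as two counts with denominators.

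**Working it through.** The plan states no figure on this point, so there is none to reproduce. The check applies the 6.5.2 rule to example values and then goes through the planned outputs.

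**Step 1: the classification rule.** Values are multiples of the upper limit of normal (ULN). All are assumed; the documents give no laboratory limits. The rule is: high if the value exceeds 1, low if it is below the lower limit (taken as 0.2), otherwise normal.

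| Baseline | Post-baseline | Cell |
|---|---|---|
| 0.8 | 1.05 | normal to high |
| 0.8 | 10 | normal to high |
| 1.1 | 1.2 | high to high |
| 1.1 | 10 | high to high |
| 3 | 20 | high to high |

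The first two rows cannot be told apart. The last three all read as no shift.

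**Step 2: two arms side by side.** The arm size of 162 is from SAP 6.1.9; everything else is assumed. In each arm 16 subjects start at 1.1 and 146 start at 0.6. Of those 146, 16 rise to 1.1, a change of 0.5. In the RHB-104 arm only, k of the 16 subjects high at baseline rise to 10, a change of 10 − 1.1 = 8.9. All other values stay put.

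The shift table is the same in both arms for every k: 130 normal to normal, 16 normal to high, 16 high to high (130 + 16 + 16 = 162).

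Mean change is (16 × 0.5 + 8.9k)/162:
- placebo: 8/162 = 0.05
- k = 2: 25.8/162 = 0.16
- k = 5: 52.5/162 = 0.32
- k = 8: 79.2/162 = 0.49

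The median change is 0 in the RHB-104 arm. The maximum change is 8.9 against 0.5 for every k. So the change-from-baseline table does signal an extreme value, but its maximum is the same for two subjects as for eight.

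**Step 3: what each planned output can show.**

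| Output | Shows an extreme value? | Counts subjects with one, by arm? |
|---|---|---|
| Shift tables 14.3.4.2 and 14.3.4.4 | No | No |
| Observed and change tables 14.3.4.1 and 14.3.4.3 | Yes, through the range | No |
| Full and flagged listings | Yes | No |
| Adverse events by maximum severity, Table 14.3.1.4 | If reported as an event | Only the reported events |

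**Step 4: by visit, not by subject.** The schedule in SAP 4.1.1 has hematology and biochemistry at weeks 2, 4, 6, 8, 12, 16, 20, 26, 35, 44, 52 and 56, which is 12 post-baseline visits. The shift is tabulated at each. A subject abnormal at one visit and another abnormal at a different visit are never added together. In addition, 6.5.2 summarises the latest value when a time point has several, so a peak followed by a repeat at the same time point would appear in the listings but not in the range.

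**The case against.** The case against is substantial. The shift tables are not the whole plan. Ranges are printed by arm and visit, every value is listed with out-of-range values marked, and adverse events are tabulated by severity, seriousness and discontinuation. Under SAP 6.6 the DSMB also reviews clinical laboratory findings during the trial. A reader might infer that the three-category tables hide toxicity. The documents do not support that: a severe individual value would be visible in several places. What remains is that none of these outputs turns such values into a by-arm count, apart from those reported as adverse events.

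A reader might also infer a specific problem with white cells, since the protocol admits subjects with "White blood cell count ≥ 3.5x10° at screening" and allows azathioprine, 6-MP or methotrexate. That needs a laboratory lower limit above 3.5, which neither document gives. The criterion applies at screening, whereas SAP 6.1.4 takes the last value before first dose as baseline. Nothing shows how many subjects would start out of range.

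Nor should p-values carry the point. SAP 6.5.2 is descriptive and plans no laboratory tests, and any p-value would follow from assumed counts: with 162 per arm, Fisher's exact test gives 0.015 for 7 against 0, 0.061 for 5 against 0, and 0.12 for 4 against 0. For shifts from normal, extra marked cases would still raise the count of high values; what is lost is their size.

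Finally, SAP 8 keeps table layouts in a separate document that was not available, so extra categories there cannot be excluded. The SAP text does not provide for them. Low, normal and high shifts are also consistent with the protocol, so this is an improvement and not the repair of a contradiction.

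**Conclusion.** The point holds in a limited form. As written, 6.5.2 gives biochemistry and hematology shift tables that cannot separate marked from trivial abnormalities and that code worsening from an out-of-range baseline as no shift. No other planned laboratory table gives the number and percentage of subjects, by arm, with a marked abnormality or with their worst post-baseline category. An imbalance would have to be assembled from listings or seen through adverse event reporting.

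Its size in this trial cannot be stated, because the documents give no laboratory limits or abnormality rates; the illustration shows the mechanism only. The conclusion assumes that the separate layouts add no graded categories. It concerns safety reporting and leaves the primary and key secondary analyses untouched. It is a low-cost improvement, not a serious fault.

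**What to change.** Keep the by-visit low, normal and high tables. Before unblinding, which SAP 6.8 allows for, amend 6.5.2 and the table list in 8.1 to add one table each for biochemistry and hematology, by arm, in the Safety Population:
- shift from baseline grade to worst post-baseline grade, using a named grading scale, or stated multiples of the normal limit for liver enzymes and bilirubin;
- n (%) of subjects worsening by two or more grades.

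State that the worst value is taken over all post-baseline results, including repeats at the same time point, and give the denominator for each parameter. Cut-offs fixed before unblinding make the result easier to rely on, whether it raises concern or reassures.

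The data are already collected. The cost is SAP wording, programming of the cut-offs and two further tables. The drawback is more low-count cells, where chance differences between arms will appear and must be read as descriptive.

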	The study is designed to assess remission at Week 26 as the primary endpoint. However, as MAP are slow growing mycobacteria without a proven antibiotic treatment, the duration of antibiotic treatment needed to achieve remission in subjects with CD caused by MAP may be longer than 26 weeks. Subjects with response at week 26 may ultimately achieve remission at a later time point with continued treatment for MAP. Also, subjects with CD treated for underlying MAP infection may experience benefits with a longer period of time in response or remission with RHB-104 treatment compared to placebo. Thus, the study is also designed to assess response, remission, and maintenance of remission in subjects on randomized treatment through week 52.				

	Blood samples will be collected at baseline and at every visit after the initial 4 weeks of treatment to test for MAP in the serum using a polymerase chain reaction (PCR) assay MAP cultures will be prepared from whole blood collected at the baseline visit and after 26 and 52 weeks of treatment.						
	Safety and pharmacokinetics of the fixed-dose combination product, RHB-104, will also be assessed.						
	Colonoscopy will be done in consenting subjects prior to initiation of study drug and after 26 weeks of study drug to assess for mucosal healing as well as MAP status via PCR and culture. Optional biopsies will also be collected for possible measurement of tissue drug levels and archived for future MAP determinations.						
	Study Visit Schedule:						
	Screening, baseline, and follow-up visits at weeks 2, 4, 6 (+/- 3 days), 8, 12, 16, 20, 26, 35, 44, 52, and 56 (+/- 7 days). Subjects undergoing colonoscopy will have a procedural visit after week 26 assessment so as to not interfere with data collection.						
Subject Participation Duration:	Subjects are expected to participate up to 62 weeks. However, subjects who complete 26 weeks of study drug administration and remain out of remission e.g. CDAI ≥150, will be eligible for open label treatment with RHB-104 in an extension study (protocol RHB-104-04). Subjects may elect to continue in the RHB-104-01 study, and will remain in the RHB-104-01 study until study drug administration in the RHB-104-04, if applicable.						
Treatment:	RHB-104; a fixed-dose combination of 95 mg clarithromycin, 45 mg rifabutin, and 10 mg clofazimine. Placebo is a capsule with a similar appearance as RHB-104.						
Route of Administration:	Oral capsule.						

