2.2.5 Safety Endpoints/Variables

Safety parameters include the following.

- Adverse events
- Incidence of uveitis
- Laboratory parameters (hematology, chemistry, urinalysis)
- Vital signs
- ECG
- Physical examination
- Concomitant medications

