4.1.1 Study Visit Schedule

	Screening (Day -42 to screening Day -7)	Baseline Day 1 / Week 0 ⁶	Week 2	Week 4	Week 6	Weeks 8, 12, 16 and 20	Week 26	Weeks 35 and 44	Week 52	Week 56
Study Visit Window			± 3 days	± 3 days	± 3 days	± 7 days	± 7 days	± 7 days	± 7 days	± 7 days
Informed Consent	X									
Inclusion/ Exclusion Criteria Demography and Medical History	X	X								
Concomitant Medications Assessment	X	X	X	X	X	X	X	X	X	X
Vital Signs and Physical Examination	X	X	X	X	X	X	X	X	X	X
Adverse Event Assessments			X	X	X	X	X	X	X	X
CDAI collection ¹		X		X		X	X	X	X	
Subject Assessments: IBDQ and SF-36		X					X		X	
Uveitis Assessment	X	X	X	X	X	X	X	X	X	X
ECG ²	X	X	X	X		Weeks 8 and 12	X		X	
Hematology and Biochemistry	X	X	X	X	X	X	X	X	X	X
Urinalysis ³	X	X	X	X	X	X	X	X	X	X
Plasma Levels of RHB-104 ⁴							X			
Hep B S Ag, Hep C Ab, HIV and QuantiFERON®-TB	X									
C-Reactive Protein (CRP)	X	X				X	X	X	X	
MAP Testing Blood with Additional Sample for Future Use		X		X		X	X	X	X	
MAP culture from blood		X					X		X	
Fecal calprotectin	X	X				Week 12	X		X	
Stool Testing other ⁵	X						X		X	
Pregnancy Test Urine	X	X	X	X	X	X	X	X	X	X
Colonoscopy ⁶ and CDEIS, storage of images, MAP testing , archive samples and possible analysis of drug levels		X					X			
Population PK Blood Sampling ⁴			X	X	X	Week 8, 12 and 20		X	X	X ⁸
Randomization (after meeting inclusion/exclusion criteria) ⁷		X								

Study Drug and Diary Dispensing (with instructions for drug administration & diary completion ¹)	Diary only	X	X	X	X	X	X	X		
Drug Return & Accountability			X	X	X	X	X	X	X	
Telephone reminder of dose escalation		Day 7	Day 21							

¹ **CDAI:** Subjects will complete a CDAI diary for the 7 days preceding their next study visit. To ensure compliance, site personnel will contact subjects prior to initiation of the CDAI-recording period, to review the process for adequate CDAI data collection. At the screening visit the 7-Day CDAI diary will be distributed to the subject for completion before the Baseline visit and if applicable, before the colonoscopy preparation/procedure takes place.

² **ECG:** Five minute continuous digital 12-lead ECG after resting 10 minutes in a supine position

³ **Urine Testing:** Dipstick test only, unless results are abnormal

⁴ **Frozen plasma sample:** For Week 26 clarithromycin, rifabutin, clofazimine, 14-hydroxy-clarithromycin, and 25-O-desacetyl-rifabutin plasma concentration measurement.

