6.5.5 Uveitis Assessment

Results from Uveitis assessments will be listed and summarized by treatment and overall as the number and percentage of subjects with Uveitis suspected (yes or no), and if suspected, with Uveitis confirmed (yes or no).

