Table 14.2.4.3.2	Week 26 Correlations Blood PCR Assay, Blood Culture Test, Colon Biopsy PCR Assay and CDAI: Intent-to-Treat Population
Table 14.2.4.3.3	Week 52 Correlations Blood PCR Assay, Blood Culture Test, Colon Biopsy PCR Assay and CDAI: Intent-to-Treat Population
Figure 14.2.4.1.1	Scatter Plot: Blood PCR Assay Level vs. CDAI Total score baseline, weeks 26 & 52: Intent-to-Treat Population
Figure 14.2.4.1.2	Scatter Plot: Blood Culture Test vs. CDAI Total score baseline, weeks 26 & 52: Intent-to-Treat Population
Figure 14.2.4.1.3	Scatter Plot: Colon Biopsy PCR Assay vs. CDAI Total score baseline, weeks 26 & 52: Intent-to-Treat Population
Exploratory Endpoints: General Other Endpoints	
Table 14.2.5.1	Proportion of subjects tapered off steroids in each treatment arm by Visit Time

	Points Post Baseline
Table 14.2.5.2	Summary Tissue Levels of Active Agents of RHB-04 in Colon Biopsy Samples by Visit Sample Time-Points Post-baseline
Adverse Events	
Table 14.3.1.1	Adverse Events Incidence Summary: Safety Population
Table 14.3.1.2	Treatment-Emergent Adverse Events by System Organ Class and Preferred Term: Safety Population
Table 14.3.1.3	Treatment-Emergent Adverse Events by System Organ Class, Preferred Term, and Relationship to Study Medication: Safety Population
Table 14.3.1.4	Treatment-Emergent Adverse Events by System Organ Class, Preferred Term, and Maximum Severity: Safety Population
Table 14.3.1.5	Treatment-Emergent Adverse Events Leading to Study Discontinuation by System Organ Class and Preferred Term: Safety Population
Table 14.3.1.6	Treatment-Emergent Serious Adverse Events by System Organ Class and Preferred Term: Safety Population
Table 14.3.1.7	Treatment-Emergent Serious Adverse Events by System Organ Class, Preferred Term, and Maximum Relationship to Study Drug: Safety Population
Table 14.3.2.1	Listing of Subjects with Adverse Events that Led to Death: Safety Population
Table 14.3.2.2	Listing Subjects with Treatment-Emergent Serious Adverse Events: Safety Population
Table 14.3.2.3	Listing Subjects with Adverse Events that Led to Study Discontinuation or Study Drug Interruption: Safety Population
Table 14.3.2.4	Listing of Subjects with Treatment-Emergent Adverse Events Related to Study Drug: Safety Population
Table 14.3.2.5	Listing of Deaths: Safety Population
Labs Assessments	
Table 14.3.4.1	Biochemistry Laboratory Data – Observed and Change from Baseline: Safety Population

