Listing 16.2.6.5	Inflammation Parameters: Intent-to-Treat Population
Listing 16.2.6.6	MAP Detection (yes/no): Intent-to-Treat Population
Listing 16.2.6.7	Endoscopic Assessment – CDEIS: Intent-to-Treat Population
Listing 16.2.6.8	Endoscopic Assessment – SES-CD: Intent-to-Treat Population
Listing 16.2.6.9	MAP Assessment – Blood PCR Assay
Listing 16.2.6.10	MAP Assessment – Blood Culture
Listing 16.2.6.11	MAP Assessment – Colon Biopsy
Listing 16.2.6.12	Inflammation Assessment – CRP marker
Listing 16.2.6.13	Inflammation Assessment – Fecal calprotectin
Listing 16.2.7.1	Adverse Events: Safety Population
Listing 16.2.8.1	Laboratory Assessments -: Biochemistry: Safety Population
Listing 16.2.8.2	Laboratory Assessments – Hematology: Safety Population
Listing 16.2.8.3	Laboratory Assessments - Urinalysis: Safety Population
Listing 16.2.9.1	Stool Samples - C. Difficile Toxin: Safety Population
Listing 16.2.9.2	Urine Pregnancy Test: Safety Population

STATISTICAL ANALYSIS PLAN

RedHill Biopharma Ltd.

RHB-104-01

Page 50

Listing 16.2.9.3	Uveitis Assessment: Safety Population
Listing 16.2.9.4.1	12-Lead ECG (Part 1): Safety Population
Listing 16.2.9.4.2	12-Lead ECG (Part 2): Safety Population
Listing 16.2.9.4.3	12-Lead ECG (Part 3): Safety Population
Listing 16.2.9.5	Vital Signs: Safety Population
Listing 16.2.9.6.1	Physical Examination at Screening: Safety Population
Listing 16.2.9.6.2	Physical Examination Significant Change from Previous Visit: Safety Population

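### As titled, the SAP's uveitis table covers 2 of 12 scheduled post-baseline assessments, so it does not give the uveitis incidence that the SAP names as a safety endpoint

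*SAP*

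**What the plan says.** - **Endpoint.** SAP 2.2.5 lists "Incidence of uveitis" as a safety variable, on its own line apart from adverse events.
- **Schedule.** SAP 4.1.1 marks the assessment in every column from screening to Week 56: "Uveitis Assessment X X X X X X X X X X". The Protocol synopsis spells out the visits: "Screening, baseline, and follow-up visits at weeks 2, 4, 6 (+/- 3 days), 8, 12, 16, 20, 26, 35, 44, 52, and 56".
- **Analysis text.** SAP 6.5.5 says that results will be listed and "summarized by treatment and overall as the number and percentage of subjects with Uveitis suspected (yes or no"), then confirmed or not among those suspected. It restricts the summary to no particular visits. It also gives no rule for combining visits, such as ever versus never after baseline.
- **Table.** SAP 8.1 has one table dedicated to uveitis, Table 14.4.2: "Uveitis Assessment at Baseline, Week 26 and Week 52: Safety Population".
- **Other outputs.** Listing 16.2.9.3, "Uveitis Assessment: Safety Population", carries no visit limit in its title. Nor does Table 14.3.1.2, "Treatment-Emergent Adverse Events by System Organ Class and Preferred Term: Safety Population".

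**The concern.** An incidence counts subjects who have the event at any time during follow-up. Status at two fixed visits is a different quantity: a case found at Week 12 and resolved by Week 26 does not show at either visit. The plan treats uveitis as important enough to check at every visit and to name separately from adverse events, yet the table that should carry the result is titled for two post-baseline time points.

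Subjects who leave early add to the gap. Someone who stops before Week 26 has no scheduled post-baseline result at a tabulated visit. The Protocol describes one such exit, since subjects who do not reach the target dose are withdrawn. It also describes a later one: subjects out of remission at Week 26 may move to the open-label extension, and those who do would have no Week 52 result here. The safety population in SAP 5 includes everyone who took a dose, but the Week 26 and Week 52 columns can reflect only those assessed then. If departures related to uveitis differ between arms, the comparison in this table would be distorted as well as incomplete.

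**Working it through.** The plan states no figure for uveitis, so there is nothing to reproduce. The check is a count of visits, followed by an illustration of what two visits can capture.

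**1. Count of assessments.** The post-baseline visits in the Protocol synopsis are Weeks 2, 4, 6, 8, 12, 16, 20, 26, 35, 44, 52 and 56, which is 12. SAP 4.1.1 marks uveitis at each of them. Table 14.4.2 names Weeks 26 and 52.

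- Used: 2 of 12.
- Outside the table: 10/12 = 83%.
- Of those 10, seven fall before Week 26 (Weeks 2, 4, 6, 8, 12, 16 and 20).

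**2. What two visits capture.** The documents give no uveitis rate, onset time or duration, so these are assumptions: onset is uniform over 52 weeks, a finding stays detectable for D weeks, and nobody drops out. A finding is present at Week 26 if it began in the D weeks before that visit, and likewise for Week 52. For D up to 26 the two windows do not overlap, so

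share captured = 2D/52 = D/26.

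**3. What all visits capture.** The gaps between successive visits from Week 0 to Week 52 are 2, 2, 2, 2, 4, 4, 4, 6, 9, 9 and 8 weeks, which sum to 52. In each gap, onsets in the last min(D, gap) weeks are still present at the visit that closes it, so

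share captured = sum of min(D, gap)/52.

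For D = 4 this is (4×2 + 3×4 + 4×4)/52 = 36/52 = 69%. For D = 8 it is (8 + 12 + 6 + 8 + 8 + 8)/52 = 50/52 = 96%.

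| Duration D (weeks) | Weeks 26 and 52 only | All scheduled visits |
|---|---|---|
| 1 | 4% | 21% |
| 2 | 8% | 42% |
| 4 | 15% | 69% |
| 8 | 31% | 96% |
| 13 | 50% | 100% |
| 20 | 77% | 100% |
| 26 | 100% | 100% |

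**4. Sensitivity.** Spreading onset over 56 weeks changes the two-visit share to 2D/56 for D up to 26, which reaches 50% at D = 14 rather than 13. Subjects missing at Week 26 or Week 52 would lower the two-visit share further.

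**5. Do other outputs supply the incidence?**

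- Listing 16.2.9.3 gives individual records, not counts and percentages by arm.
- The treatment-emergent adverse event tables count each subject once per preferred term with no visit limit, so they give an incidence for whatever is recorded as an adverse event. The documents do not say that suspected or confirmed uveitis must be recorded as one, and these tables do not carry the split between suspected and confirmed that SAP 6.5.5 calls for.

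**The case against.** The strongest reply is that this is a title narrower than its text, and that no data are excluded. SAP 6.5.5 governs the analysis, sets no visit limit and describes a subject-level summary. SAP 8 puts the shells in a separate document and allows layouts to change without amending the SAP, so the rows and denominators of Table 14.4.2 cannot be read from its title. Titles elsewhere are also loose: Table 14.4.1 names only Weeks 26 and 52 for vital signs, while SAP 6.5.3 plans them by visit.

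Most of that stands, and it limits the point to what the title implies. It does not remove the point, because no listed table is titled for uveitis at any post-baseline visit and SAP 6.5.5 has no rule that would produce one.

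Three stronger readings are tempting, and the documents do not support them:

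- **That most events are missed, or that only 2/12 = 17% are shown.** The 17% requires equal detection at visits spaced 2 to 9 weeks apart and resolution before the next visit. Under uniform onset, most events are missed only if findings last less than about 13 to 14 weeks, and the duration is not given.
- **That these events go uncounted in the study report.** They are absent from the post-baseline columns of one table. The listing holds them, and the adverse event tables hold those recorded as adverse events.
- **That subjects who stopped because of uveitis are the most under-reported.** Table 14.3.1.5 and the listing numbered Table 14.3.2.3 cover adverse events leading to discontinuation, and an event that ends participation is a likely one to be recorded there. Early leavers also remain in the safety population and in the baseline column.

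**Conclusion.** The point holds as a reporting gap. A named safety endpoint has no planned table that, as titled, estimates it: Table 14.4.2 uses 2 of 12 scheduled post-baseline assessments and falls short of both SAP 2.2.5 and SAP 6.5.5.

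The visit count is firm. The share of findings missed is not, because it ranges from nearly all (4% captured at 1 week) to none (100% captured at 26 weeks), under assumed uniform onset over 52 weeks and no dropout. The conclusion also rests on the table title, since the shell is not in these documents. Data collection, the planned adverse event reporting and the primary efficacy analysis are not in question. It is worth correcting because the remedy is nearly free and no other listed output reliably replaces the missing summary.

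**What to change.** Add to Table 14.4.2, by arm and overall, the number and percentage of subjects with suspected uveitis, and with confirmed uveitis, at any post-baseline assessment (scheduled, unscheduled or early termination). Use all treated subjects as the denominator. Keep the by-visit rows, preferably for all 12 visits, and change the title to match. Put the any-post-baseline rule in SAP 6.5.5, and state there whether confirmed uveitis is also recorded as an adverse event, so that the two sets of tables can be reconciled.

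Settle this before unblinding rather than using the freedom in SAP 8 to adjust layouts once data have been seen. The cost is one table shell and a sentence or two of SAP text. The scheduled assessments are already collected, and the efficacy analyses do not change.
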